8.2 Safety and Other Assessments

Study procedures are specified in the SOA. A study physician licensed to make medical diagnoses and listed on the 1572 will be responsible for all trial-related medical decisions.

Physical examination:

A targeted physical examination will be performed at baseline prior to initial infusion on Day 1. The baseline physical examination can be one that is conducted from screening to Day 1. Post-baseline physical examinations will be done only when needed to evaluate possible adverse event(s) (i.e. any new signs or symptoms). No routine physical exam is needed for study visits after Day 1.

Study staff at some sites are not allowed into the subject's rooms due to a limited supply of PPE and the need for strict respiratory isolation measures for COVID-19 patients. Because of limited access to subjects, physical exams can be performed by any licensed provider at the study hospital even if they are not study staff listed on the 1572. The study team can extract information from the hospital chart or EMR.

Clinical laboratory evaluations:

- Fasting is not required before collection of laboratory samples.
- Blood will be collected at the time points indicated in the SOA.
 - Clinical safety laboratory tests include WBC, differential, Hgb, PLT, creatinine, glucose, total bilirubin, AST, ALT, and PT. Sites that do not have access to a test for PT will be allowed to report an international normalized ratio (INR).
 - Day 1 clinical laboratory evaluations are drawn prior to initial infusion as a baseline and results do not need to be reviewed to determine if initial infusion should be given.
- Clinical laboratory testing will be performed at each clinical trial site in real time.

Table 3. Venipuncture Volumes¹

	Screen	Baseline						
Day +/- Window	-1 to 1	1 ± 1	3 ± 1	5 ± 1	8 ± 1	11 ± 1	15 ± 2	29 ± 3
Safety hematology, chemistry and liver tests	X 10mL ²	X 10mL ²	X 10mL ²	X 10mL ²	X 10mL ²	X 10mL ²	X ³ 10mL ²	X ³ 10mL ²
Blood for Serum		X 24mL	X 24mL	X 24mL	X 24mL	X 24mL	X 24mL	X 24mL
Plasma (includes PCR)		X 8mL	X 8mL	X 8mL	X 8mL	X 8mL		
Total volume	10mL	42ml	42mL	42ml	42ml	42ml	34mL	34mL
Total all study days								268~288 mL

1. See SOA in Section 1.2 for specific tests to be performed.

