8.3 Adverse Events and Serious Adverse Events

8.3.1 Definition of Adverse Event (AE)

AE means any untoward medical occurrence associated with the use of an intervention in humans, whether or not considered intervention-related. An AE can therefore be any unfavorable and unintended sign (including an abnormal laboratory finding), symptom, or disease temporally associated with the use of medicinal (investigational) product.

Any medical condition that is present at the time that the subject is screened will be considered as baseline and not reported as an AE. However, if the severity of any pre-existing medical condition increases to severity level 3 or 4, it should be recorded as an AE.

Given the nature of severity of the underlying illness, subjects will have many symptoms and abnormalities in vital signs and laboratory values. All Grade 3 and 4 AEs will be captured as

AEs in this trial. In addition, any Grade 2 or higher, suspected drug-related hypersensitivity reaction will be reported as an AE in this trial (see Section 7.1.1).

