3.3. Study Definitions and Derived Variables

3.3.1. Baseline Value

For efficacy assessments, the baseline value will be defined as the last value obtained prior to randomization. For safety assessments, the baseline value will be defined as the last value obtained prior to the first dose of study product.

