9.6. Clinical Laboratory Evaluations

Clinical safety laboratory adverse events are collected Day 1, 3, 5, 8, 11 and Day 15 and 29 if able to return to clinic or still hospitalized. Parameters evaluated include white blood cell count, absolute neutrophil count, eGFR, platelet count, hemoglobin concentration, creatinine, glucose, total bilirubin, ALT, AST, and PT/INR. Laboratory safety parameters will be graded according to the Division of AIDS (DAIDS) Table for Grading the Severity of Adult and Pediatric Adverse Events, version 2.1 (July 2017).

The distribution of Grade 3 and 4 chemistry and hematology laboratory results by maximum severity, time point, disease severity and treatment group will be presented (Table 65).

Descriptive statistics including mean, median, standard deviation, maximum, and minimum values and change from baseline by time point, for all and each chemistry and hematology laboratory parameter will be summarized by disease severity and treatment arm (Table 66). Changes in chemistry and hematology laboratory values will be presented in line graphs over time with mean and SD plotted by disease severity and treatment arm (Figure 25).

Listings will provide a complete listing of individual chemistry and hematology laboratory results with applicable reference ranges (Listing 19).

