n = Number of subjects who died or experienced SAEs, Grade 3 or 4 AEs, or Discontinuation of Study Infusions.

HR is the hazard ratio from the Cox Model

P-value calculated using the Log-rank test

Table 65: Abnormal Laboratory Results of Grade 3 or 4 by Parameter, Maximum Severity, Time Point, and Treatment Group – Treated Population

Laboratory Parameter	Time Point	Treatment Group	N	Severe/ Grade 3		Life Threatening/ Grade 4	
				n	%	n	%
Any Parameter	Baseline	Remdesivir	x	x	x	x	x
		Placebo	x	x	x	x	x
	Day 3	Remdesivir	x	x	x	x	x
		Placebo	x	x	x	x	x
	Day 5	Remdesivir	x	x	x	x	x
		Placebo	x	x	x	x	x
	Day 8	Remdesivir	x	x	x	x	x
		Placebo	x	x	x	x	x
	Day 11	Remdesivir	x	x	x	x	x
		Placebo	x	x	x	x	x
	Day 15	Remdesivir	x	x	x	x	x
		Placebo	x	x	x	x	x
	Day 29	Remdesivir	x	x	x	x	x
		Placebo	x	x	x	x	x
	Maximum Severity Post Baseline	Remdesivir	x	x	x	x	x
		Placebo	x	x	x	x	x

Each parameter will be summarized individually similar to the above...

The “Max Post Baseline” rows indicate the maximum severity experienced by each subject at any time point post baseline, including unscheduled assessments.

N = Number of subjects in the Treated Population

Table 66: Summary Statistics of Laboratory Results by Parameter, Study Visit Day, and Treatment Group – Treated Population

Laboratory Parameter	Study Visit Day	Treatment Group	Absolute					Change from Baseline				
			N	Mean	SD	Median	Min, Max	N	Mean	SD	Median	Min, Max
Parameter 1	Baseline	Remdesivir	x	xx.x	xx.x	xx.x	xx.x, xx.x	---	---	---	---	---
		Placebo	x	xx.x	xx.x	xx.x	xx.x, xx.x	---	---	---	---	---
	Day 3	Remdesivir	x	xx.x	xx.x	xx.x	xx.x, xx.x	x	xx.x	xx.x	xx.x	xx.x, xx.x
		Placebo	x	xx.x	xx.x	xx.x	xx.x, xx.x	x	xx.x	xx.x	xx.x	xx.x, xx.x
	Day 5	Remdesivir	x	xx.x	xx.x	xx.x	xx.x, xx.x	x	xx.x	xx.x	xx.x	xx.x, xx.x
		Placebo	x	xx.x	xx.x	xx.x	xx.x, xx.x	x	xx.x	xx.x	xx.x	xx.x, xx.x
	Day 8	Remdesivir	x	xx.x	xx.x	xx.x	xx.x, xx.x	x	xx.x	xx.x	xx.x	xx.x, xx.x
		Placebo	x	xx.x	xx.x	xx.x	xx.x, xx.x	x	xx.x	xx.x	xx.x	xx.x, xx.x
	Day 11	Remdesivir	x	xx.x	xx.x	xx.x	xx.x, xx.x	x	xx.x	xx.x	xx.x	xx.x, xx.x
		Placebo	x	xx.x	xx.x	xx.x	xx.x, xx.x	x	xx.x	xx.x	xx.x	xx.x, xx.x
	Day 15	Remdesivir	x	xx.x	xx.x	xx.x	xx.x, xx.x	x	xx.x	xx.x	xx.x	xx.x, xx.x
		Placebo	x	xx.x	xx.x	xx.x	xx.x, xx.x	x	xx.x	xx.x	xx.x	xx.x, xx.x
	Day 29	Remdesivir	x	xx.x	xx.x	xx.x	xx.x, xx.x	x	xx.x	xx.x	xx.x	xx.x, xx.x
		Placebo	x	xx.x	xx.x	xx.x	xx.x, xx.x	x	xx.x	xx.x	xx.x	xx.x, xx.x

Continue for all parameters...

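### SAP Table 65 counts persistent pre-dose Grade 3/4 laboratory values together with new ones, which blurs the between-arm contrast for new laboratory toxicity (minor)

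*SAP*

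**What the plan says.** SAP 9.6 (Clinical Laboratory Evaluations) introduces Table 65: "The distribution of Grade 3 and 4 chemistry and hematology laboratory results by maximum severity, time point, disease severity and treatment group will be presented". The shell in SAP Appendix 1 has rows for baseline, for each scheduled visit and for maximum severity after baseline, with Grade 3 and Grade 4 columns by arm. It gives these first for any parameter and then for each parameter. The footnote says that the maximum post-baseline "rows indicate the maximum severity experienced by each subject at any time point post baseline, including unscheduled assessments". The denominator footnote reads "N = Number of subjects in the Treated Population". Neither place sets a worsening or treatment-emergent condition.

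Elsewhere the plan does use a baseline. SAP 3.3.1 states: "For safety assessments, the baseline value will be defined as the last value obtained prior to the first dose of study product". Protocol 8.3.1 treats conditions present at screening as baseline and not as adverse events, with the exception that "if the severity of any pre-existing medical condition increases to severity level 3 or 4, it should be recorded as an AE".

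The protocol also expects abnormal values at entry. Section 8.3.1 says that "subjects will have many symptoms and abnormalities in vital signs and laboratory values". Section 8.2 says of the Day 1 laboratory tests that "results do not need to be reviewed to determine if initial infusion should be given".

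**The concern.** Table 65 is where a reader will look for severe laboratory abnormalities by arm and by parameter. In acutely ill inpatients, some Grade 3/4 values after baseline continue what was there before dosing. The maximum post-baseline row adds these to the new cases. A common background count in both arms makes a true excess on active drug look relatively smaller.

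The any-parameter row is the most exposed. A subject already counted for a persistent Grade 3 glucose adds nothing when a new Grade 3 creatinine appears.

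Protocol 2.3.2 names transaminase elevation, mild PT prolongation and (from animal studies) kidney injury as matters to watch, so a clear display of new laboratory toxicity has some value. The other planned laboratory summaries do not supply it. The baseline rows of Table 65 are marginal counts that do not link a subject's grades. Table 66 and Figure 25 give summary statistics and mean changes, not grade shifts.

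**Working it through.** The plan states no figure for Table 65, so there is none to reproduce. The check is a small model of what the row counts.

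**Inputs from the documents.** The row takes the worst post-baseline grade with no baseline condition, over all Treated subjects (Table 65 footnotes). Allocation is 1:1 (protocol 6.3), so equal baseline shares are the expected case.

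**Assumed inputs, because the documents give none.**
- b: share already Grade 3/4 at baseline, equal in the two arms.
- s: chance that such a subject is Grade 3/4 again after baseline.
- p: new-onset risk in the others, 15% on active and 10% on placebo (risk ratio 1.50, difference 5.0 points).

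**Formula.** Displayed rate = b·s + (1-b)·p. With equal b and s the first term cancels from the difference, so displayed difference = (1-b)·(15% - 10%).

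**Equal persistence.** For example, at b=30% and s=1, active is 0.30 + 0.70×0.15 = 40.5% and placebo is 0.30 + 0.70×0.10 = 37.0%.

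| b | s | Active | Placebo | Difference (points) | Risk ratio |
|---|---|---|---|---|---|
| 0% | – | 15.0% | 10.0% | 5.0 | 1.50 |
| 5% | 1 | 19.25% | 14.5% | 4.75 | 1.33 |
| 10% | 1 | 23.5% | 19.0% | 4.5 | 1.24 |
| 10% | 0.5 | 18.5% | 14.0% | 4.5 | 1.32 |
| 30% | 1 | 40.5% | 37.0% | 3.5 | 1.09 |
| 30% | 0.5 | 25.5% | 22.0% | 3.5 | 1.16 |
| 40% | 1 | 49.0% | 46.0% | 3.0 | 1.07 |

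**Unequal persistence, b=20%.** New onset contributes 0.80×0.15 = 12 points on active and 0.80×0.10 = 8 points on placebo.
- s=1 in both arms: 32% v 28%, risk ratio 1.14.
- s=0.7 active, 0.9 placebo: 14+12 = 26% v 18+8 = 26%. The excess disappears.
- s=0.5 active, 0.9 placebo: 10+12 = 22% v 18+8 = 26%, risk ratio 0.85. The contrast reverses.
- s=0.9 active, 0.7 placebo: 18+12 = 30% v 14+8 = 22%. The difference is 8 points, above the true 5.0.

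**Does a worsening flag alone repair it?** Over all Treated subjects, the flagged rate is (1-b)·p. At b=30% that is 0.70×0.15 = 10.5% v 0.70×0.10 = 7.0%. The risk ratio is back to 1.50, but the difference is still 3.5 points, as in the present row. Only with an at-risk denominator (baseline below Grade 3) does the row show 15% v 10%, with difference 5.0 and risk ratio 1.50, at every b.

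**The case against.** The strongest reply is that this is a matter of display. Table 65 has no test. With no drug effect and equal persistence, the row is equal in expectation between arms, so it creates no false signal. A count regardless of baseline also has its own use as a measure of total burden. Severe laboratory events that worsen from baseline are already meant to be captured as adverse events under protocol 8.3.1. They then enter Table 63 (with Barnard's exact test), the time-to-event composite in Table 64, and Table 58 when a preferred term reaches 5%. Listing 19 shows every result with its toxicity grade by subject and time point, and SAP section 17 allows extra tables.

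Most of this stands, and it rules out several stronger readings that a reader might infer:
- *That new and persistent cases can never be separated.* Listing 19 links them; what is missing is a summary.
- *That Table 65 is the only comparison of severe laboratory events.* The adverse event tables give partial cover.
- *That a comparison loses power.* No test is planned on this table, so there is none to lose.
- *That the row counts the pre-dose values.* Those have their own row. It counts later values in subjects who were already Grade 3/4.
- *That a real difference is always hidden.* The contrast shrinks by a factor that may be close to 1, and with unequal persistence it can move either way.

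The cover from adverse events is incomplete. Tables 63 and 64 pool all Grade 3/4 events, and protocol 8.3.5.1 has a laboratory abnormality that belongs to a syndrome recorded as the diagnosis. A comparison by parameter would have to be rebuilt by hand from the listing.

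**Conclusion.** The point holds as a minor one. No planned summary of graded laboratory values separates new from persistent Grade 3/4 cases by arm, and the maximum post-baseline row mixes them.

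The size depends on b and on persistence, which the documents do not give. Under the assumed 15% v 10% and full persistence, a risk ratio of 1.50 would display as 1.33 at b=5%, 1.24 at b=10% and 1.09 at b=30%. Movement toward no difference assumes equal baseline shares and equal persistence. Randomization supports the first in expectation but does not guarantee the second.

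The effect should be largest for the any-parameter row and for parameters with no entry limit: PT, bilirubin, hemoglobin, platelets, WBC and glucose. It should be smaller for ALT/AST and renal function, because entry excludes ALT or AST above 5 times the upper limit of normal and eGFR below 30 ml/min. The documents do not reproduce the grading table, so how those limits line up with Grade 3 was not checked. No primary or key secondary result is affected.

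**What to change.** Keep the present row, labelled 'any, regardless of baseline', and add the following.

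1. **A treatment-emergent row.** Derive it for each parameter first: the worst post-baseline grade is 3 or 4 and higher than that parameter's own baseline grade. Then roll up to any parameter, counting a subject flagged on at least one. Deriving it the other way round would drop a subject with Grade 3 glucose at baseline who newly develops a Grade 3 value in another parameter.
2. **An at-risk denominator for each parameter.** Use Treated subjects with a post-baseline value whose baseline is below Grade 3 (for new Grade 3/4) or below Grade 4 (for new Grade 4). Apply the same restriction to the numerator, so that a move from Grade 3 to Grade 4 appears only under new Grade 4. State the matching rule for the any-parameter row.
3. **A stated convention for missing baseline values.**
4. **A shift table** of baseline by worst post-baseline grade (0-2, 3, 4), by arm and parameter. It also shows whether persistence differs between arms.

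The data are already collected and graded. The cost is a little more programming and one missing-baseline convention.

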[figure not shown]
Figure 22: Incidence of Non-Serious Related Unsolicited Adverse Events by MedDRA System Organ Class, Severity, and Treatment Group - Treated Population109

Figure 23: Kaplan-Meier Curve of Time to Death through Day 29 by Treatment Group – Treated Population.....110

Figure 24: Kaplan-Meier Curve of Time to Death, SAE, Discontinuation of Study Infusions or Grade 3 or 4 AE through Day 29 by Treatment Group – Treated Population111

[figure not shown]
Figure 25: [Parameter X] Results by Scheduled Visits: Mean Changes from Baseline by Treatment Group – Treated Population112

Figure 1: CONSORT Flow Diagram

Implementation Note: Disease Stratum boxes will be included in the final CONSORT diagram.

Figure 2: Kaplan-Meier Curves of Time to Recovery by Treatment Group – ITT Population

[figure not shown]
Figures with similar format:

Figure 3: Kaplan-Meier Curve of Time to Recovery by Treatment Group – Treated Population

Figure 4: Kaplan-Meier Curve of Time to Recovery by Treatment Group and Disease Severity – ITT Population

Figure 5: Kaplan-Meier Curve of Time to Recovery by Treatment Group and Disease Severity – Treated Population

Figure 6: Forest Plot of Hazard Ratios of Time to Recovery by Subgroup - ITT Population

Figures with similar format:

Figure 7: Forest Plot of Hazard Ratios of Time to Recovery by Subgroup - Treated Population

Figure 8: Forest Plot of Hazard Ratios of Time to Recovery: Leave One Site Out Sensitivity Analysis - ITT Population

Figure 9: Clinical Status Scores by Study Day – Placebo Recipients

[Shell not provided. The figure will be a spaghetti plot of clinical status scores by actual study day (of the assessment). Lines for subjects who are not retreated with remdesivir will be a muted gray color while the lines for subjects who are retreated with remdesivir will be a bold red or black color].

Figure 10: Predicted Probabilities of Scale Rating at Day 15 by Treatment Group and Disease Severity – ITT Population

[figure not shown]

Figure 11: Kaplan-Meier Curves of Time to Improvement by at least One Category of Clinical Status Score by Treatment Group – ITT Population

[figure not shown]
[figure not shown]

Figure with similar format:

[figure not shown]
Figure 12: Kaplan-Meier Curves of Time to Improvement by at least Two Categories of Clinical Status Score by Treatment Group – ITT Population

Figure 13: Distribution of Clinical Status Scores By Day by Treatment Group – ITT Population

Implementation Note: Heat map coloring will be used for the clinical score scale.

Figure 14: Bar Plots of Clinical Status Scores by Study Day and Treatment Group – ITT Population

Implementation Note: Each panel will contain bars for Remdesivir and Placebo.

Figure 15: Kaplan-Meier Curves of Time to Discharge or NEWS ≤ 2 by Treatment Group – ITT Population

[figure not shown]

Figure 16: Mean NEWS by Day and Treatment Group – ITT Population

[figure not shown]
[figure not shown]

Figure 17: Bee Swarm Plot of Oxygen Days by Treatment Group – ITT Population

Implementation Note: Death swarm will be presented as a circle or similar shape instead of a line.

Figures with similar format:

Figure 18: Bee Swarm Plot of Non-invasive Ventilation/High-Flow Oxygen Days by Treatment Group – ITT Population

Figure 19: Bee Swarm Plot of Invasive Mechanical Ventilation/ECMO Days by Treatment Group – ITT Population

Figure 20: Bee Swarm Plot of Hospitalization Days by Treatment Group – ITT Population

Figure 21: Frequency of Non-Serious Related Unsolicited Adverse Events by MedDRA System Organ Class, Severity, and Treatment Group - Treated Population

[figure not shown]

Figure 22: Incidence of Non-Serious Related Unsolicited Adverse Events by MedDRA System Organ Class, Severity, and Treatment Group - Treated Population

[figure not shown]

Figure 23: Kaplan-Meier Curve of Time to Death through Day 29 by Treatment Group – Treated Population

[figure not shown]

Figure 24: Kaplan-Meier Curve of Time to Death, SAE, Discontinuation of Study Infusions or Grade 3 or 4 AE through Day 29 by Treatment Group – Treated Population

[figure not shown]
[figure not shown]

Figure 25: [Parameter X] Results by Scheduled Visits: Mean Changes from Baseline by Treatment Group – Treated Population

APPENDIX 3. LISTINGS MOCK-UPS**TABLE OF LISTINGS**

Listing 1: Analysis Population Inclusions/Exclusions for Randomized Subjects	114
Listing 2: Subjects who Early Terminated or Discontinued Treatment.....	115
Listing 3: Subject-Specific Protocol Deviations	116
Listing 4: Non-Subject-Specific Protocol Deviations.....	117
Listing 5: Individual Efficacy Response Data: Clinical Status Score Data	118
Listing 6: Individual Efficacy Response Data: NEWS	119
Listing 7: Demographic Data	120
Listing 8: Pre-Existing and Concurrent Medical Conditions.....	121
Listing 9: Concomitant Medications.....	122
Listing 10: Compliance Data	123
Listing 11: Listing of Non-Serious Adverse Events	124
Listing 12: Listing of Non-Fatal Serious Adverse Events	125
Listing 13: Listing of Deaths.....	126
Listing 14: Pregnancy Reports – Maternal Information	127
Listing 15: Pregnancy Reports – Gravida and Para	128
Listing 16: Pregnancy Reports – Live Birth Outcomes	129
Listing 17: Pregnancy Reports – Still Birth Outcomes	130
Listing 18: Pregnancy Reports – Spontaneous, Elective, or Therapeutic Abortion Outcomes	131
Listing 19: Clinical Laboratory Results.....	132
Listing 20: Physical Exam Findings	133

Listing 1: Analysis Population Inclusions/Exclusions for Randomized Subjects

Treatment Group	Subject ID	Analysis Population	Included in Population?	Reason Subject Excluded	Included in Early Analysis Set?
Remdesivir/Placebo	XXXXX	Intent-to-Treat	Yes/No	NA/xxxxxxxxx	Yes
		Treated	Yes/No	NA/xxxxxxxxx	

Programming Notes: Include randomized subjects only. Sort Order = Treatment Group, USUBJID. If subject was included in the early analysis set, then display “Yes”. Otherwise do not display anything.

Listing 2: Subjects who Early Terminated or Discontinued Treatment

Treatment Group	Subject ID	Category	Reason for Early Termination or Treatment Discontinuation	Study Day
Remdesivir/Placebo	XXXXX	Early Termination/Treatment Discontinuation	xxxxxx	xxxx

Programming Notes: Sort Order = Treatment Group, USUBJID, category where Treatment discontinuation is sorted prior to Early termination. If the subject discontinued treatment because they were unblinded and crossover treated with remdesivir, then the reason for discontinuation will display “Treated with Remdesivir”.

Listing 3: Subject-Specific Protocol Deviations

Treatment Group	Disease Severity	Subject ID	DV Number	Deviation	Deviation Category	Study Day	Reason for Deviation	Deviation Resulted in AE?	Deviation Resulted in Subject Termination?	Deviation Affected Product Stability?	Comments
Remdesivir/Placebo	Mild/Moderate / Severe	xxxxx	xx	xxx	xxx	x	xxxx	Yes/No	Yes/No	Yes/No	xxxx

Programming Notes: Sort Order = Treatment Group, USUBJID, Deviation Number

Listing 4: Non-Subject-Specific Protocol Deviations

Site	Start Date	End Date	Deviation	Reason for Deviation	Deviation Resulted in Subject Termination?	Deviation Affected Product Stability?	Deviation Category	Comments
Xxxx	xxxx	xxxx	xxxx	xxxx	Yes/No	Yes/No	xxxx	xxxxx

Programming Notes: Sort Order = Site, start date, deviation

Listing 5: Individual Efficacy Response Data: Clinical Status Score Data

Treatment Group	Disease Severity	Subject ID	Study Visit Day of Assessment	Actual Study Day of Assessment	Clinical Status Score	Clinical Status	Included in Early Analysis Set?
Remdesivir/Placebo	Mild/Moderate / Severe	xxxxx	xx	xx	xx	xxxxx	Yes

Programming Notes: Sort Order = Treatment Group, USUBJID, Study Day. Clinical status should match the wording of the scale definitions in Section 4.3. If the record was included in the early analysis set, then display “Yes”. Otherwise do not display anything.

Listing 6: Individual Efficacy Response Data: NEWS

Treatment Group	Disease Severity	Subject ID	Study Visit Day	Actual Study Day	Respiratory Rate Score	O ₂ Saturation Score	Any Supplemental O ₂ Score	Temperature Score	Systolic BP Score	Heart Rate Score	Level of Consciousness Score	Total Score
Remdesivir/Placebo	Mild/Moderate / Severe	xxxxx	xx	xx	xx	xx	xx	xx	xx	xx	xx	xx

Programming Notes: Sort Order = Treatment Group, USUBJID, Study Day

Listing 7: Demographic Data

Treatment Group	Disease Severity	Subject ID	Geographic Region	Sex	Age at Enrollment (years)	Ethnicity	Race	Duration of Symptoms prior to Enrollment	Weight (Kg)	Height (Cm)	BMI	Included in Early Analysis Set?
Remdesivir/Placebo	Mild/Moderate / Severe	xxxxx	xxx	xxx	xx	xxx	xxx	xxx	xx	xx	xxx	Yes

Programming Notes: Sort Order = Treatment Group, USUBJID. If subject was included in the early analysis set, then display “Yes”. Otherwise do not display anything.

Listing 8: Pre-Existing and Concurrent Medical Conditions

Treatment Group	Subject ID	MH Number	Medical History Term	MedDRA System Organ Class	MedDRA Preferred Term
Remdesivir/Placebo	xxx	xx	xxxxx	xxxx	xxxx

Programming Notes: Sort Order = Treatment Group, USUBJID, MH Number

Listing 9: Concomitant Medications

Treatment Group	Subject ID	CM Number	Medication	Medication Start Day	Medication End Day	Indication	Taken for an AE? (AE Description; Number)	Taken for a condition on Medical History? (MH Description; Number)	ATC Level 1 (ATC Level 2)	Prohibited Medication?
Remdesivir/Placebo	xxx	xx	xxxx	x	x	xxxx	Yes/No	Yes/No	xxxx / xxxx	Yes/No

Programming Notes: Sort Order = Treatment Group, USUBJID, CM number

Note: If medication started prior to enrollment and there is no date, then Medication Start Day = Prior to Enrollment

If medication is ongoing at end of study, the Medication End Day = Ongoing

The “Prohibited Medication?” column refers to whether the medication falls under one of the categories of prohibited medications listed in Section 6.4.

Listing 10: Compliance Data

Category	Number of Doses	Reason for Missing, Halting or Slowing any doses	Study Day of Discharge	Study Day of Death
Treatment Group: , Subject ID:				
Received	xx	--	Xxx/NA	Xxx/NA
Missed	xx	xxxxxx		
Halted/Slowed	xx	xxxxxx		

Programming Notes: Sort Order = Treatment Group, USUBJID.

Listing 11: Listing of Non-Serious Adverse Events

Adverse Event	Study Day	Duration	Severity	Relationship to Study Treatment	If Not Related, Alternative Etiology	Action Taken with Study Treatment	Subject Discontinued Due to AE	Outcome	MedDRA System Organ Class	MedDRA Preferred Term	Included in Early Analysis Set?
Treatment Group: Subject ID: , Disease Severity: , AE Number:											
xxx	xx	x	xxx	Related/Not Related	xxxx	xxx	Yes/No	xxxx	xxxx	xxxx	Yes
Comments: xxxx											

Programming Note: Sort order will be Treatment Group, USUBJID, AE Number. If the event was included in the early analysis set, then display “Yes”. Otherwise do not display anything.

Listing 12: Listing of Non-Fatal Serious Adverse Events

Adverse Event	Study Day	Duration	No. of Days Post Dose the Event Became Serious	Reason Reported as an SAE	Severity	Relationship to Study Treatment	If Not Related, Alternative Etiology	Action Taken with Study Treatment	Subject Discontinued Due to AE	Outcome	MedDRA System Organ Class	MedDRA Preferred Term	Included in Early Analysis Set?
Treatment Group: Subject ID: , AE Number:													
xxxx	x	x	x	xxxxx	xxx	Related/Not Related	xxxx	xxxx	Yes/No	xxxxx	xxxxx	xxxxx	Yes
Comments: xxxx													

Programming Note: Sort order will be Treatment Group, USUBJID, AE Number. If the event was included in the early analysis set, then display “Yes”. Otherwise do not display anything.

Listing 13: Listing of Deaths

Adverse Event	Study Day	Duration	No. of Days Post Dose the Event Became Serious	Reason Reported as an SAE	Severity	Relationship to Study Treatment	If Not Related, Alternative Etiology	Action Taken with Study Treatment	Subject Discontinued Due to AE	MedDRA System Organ Class	MedDRA Preferred Term	Included in Early Analysis Set?
Treatment Group: Subject ID: , AE Number:												
xxxx	x	x	x	xxxxx	xxx	Related/Not Related	xxxx	xxxx	Yes/No	xxxxx	xxxxx	Yes
Comments: xxxx												

Programming Note: If the event was included in the early analysis set, then display “Yes”. Otherwise do not display anything.

Listing 14: Pregnancy Reports – Maternal Information

Treatment Group	Subject ID	Pregnancy Number	Study Day Corresponding to Estimated Date of Conception	Source of Maternal Information	Pregnancy Status	Mother's Pre-Pregnancy BMI	Mother's Weight Gain During Pregnancy	Tobacco, Alcohol, or Drug Use During Pregnancy?	Medications During Pregnancy?	Maternal Complications During Pregnancy?	Maternal Complications During Labor, Delivery, or Post-Partum?

Maternal Complications are included in the Adverse Event listing. Medications taken during pregnancy are included in the Concomitant Medications Listing.

Listing 15: Pregnancy Reports – Gravida and Para

Subject ID	Pregnancy Number	Gravida	Live Births									Still Births	Spontaneous Abortion/Miscarriage	Elective Abortions	Therapeutic Abortions	Major Congenital Anomaly with Previous Pregnancy?
			Extremely PB ^a	Very Early PB ^a	Early PB ^a	Late PB ^a	Early TB ^b	Full TB ^b	Late TB ^b	Post TB ^b						

Gravida includes the current pregnancy, para events do not.

^a Preterm Birth

^b Term Birth

Listing 16: Pregnancy Reports – Live Birth Outcomes

Subject ID	Pregnancy Number	Fetus Number	Pregnancy Outcome (for this Fetus)	Fetal Distress During Labor and Delivery?	Delivery Method	Gestational Age at Live Birth	Size for Gestational Age	Apgar Score, 1 minute	Apgar Score, 5 minutes	Cord pH	Congenital Anomalies?	Illnesses/ Hospitalizations within 1 Month of Birth?

Congenital Anomalies are included in the Adverse Event listing.

Listing 17: Pregnancy Reports – Still Birth Outcomes

Subject ID	Date of Initial Report	Fetus Number	Pregnancy Outcome (for this Fetus)	Fetal Distress During Labor and Delivery?	Delivery Method	Gestational Age at Still Birth	Size for Gestational Age	Cord pH	Congenital Anomalies?	Autopsy Performed?	If Autopsy, Etiology for Still Birth Identified?

Listing 18: Pregnancy Reports – Spontaneous, Elective, or Therapeutic Abortion Outcomes

Subject ID	Date of Initial Report	Fetus Number	Pregnancy Outcome (for this Fetus)	Gestational Age at Termination	Abnormality in Product of Conception?	Reason for Therapeutic Abortion

Listing 19: Clinical Laboratory Results

Treatment Group	Subject ID	Planned Time Point	Actual Study Day	Sex	Age (years)	Laboratory Parameter (Units)	Result (Toxicity Grade)	Reference Range Low	Reference Range High
Remdesivir/Placebo	xxx	xx	xx	xx	x	xxx (xxx)	xxx (xxxx)	xxxx	xxxx

Listing 20: Physical Exam Findings

Treatment Group	Subject ID	Planned Study Day	Actual Study Day	Body System	Abnormal Finding	Reported as an AE? (AE Description; Number)
Remdesivir/Placebo	xxx	xx	xx	xxxx	xxxxxx	Yes/No/NA

Implementation Note: For respiratory findings denoted as 'Yes' on the Physical Exam CRF, denote the Body System as "Respiratory Finding" and denote the Abnormal Finding as the symptom name; e.g. if Wheezing is reported, the Abnormal Finding will be 'Wheezing'. The Reported as an AE cell will be denoted as 'NA' for respiratory findings. Each reported respiratory finding will appear in its own row.

Sort order will be treatment group, subject ID, planned time point, and body system.
